9.6 FlowMet-R Assessment

FlowMet-R measurements will be taken before noninvasive testing as detailed in Event Schedule A. Clinical personnel must be trained on use of the FlowMet-R device prior to measurement. Details of the measurement acquisition procedure are as follows:

- A patient rest period shall be performed in accordance with standard ABI collection before FlowMet-R or ABI measurement. Extremity blood flow measurements will be performed using the FlowMet-R device in the following order: index finger of the upper right hand (if the index finger is unavailable another finger may be used), and on the great toe (if the great toe is not available the 2nd toe may be used, and this will be noted in the CRF) of the limbs being measured. If measuring bilaterally, the right side will be performed first.
- Once the probe is placed on the digit, flow will be allowed to equilibrate for approximately 30 seconds before checking signal quality to allow transient changes in perfusion to diminish. Signal quality will be confirmed by observing the presence of a pulse waveform (if one is expected), or by the stability of the flatline (in the case of complete occlusion). The clinician will also ensure that an appropriate amount of light is detected by the FlowMet-R device. The following light intensity values are acceptable: maximum intensity greater than 30 but less than 255 and average intensity greater than 25 but less than 200. The FlowMet-R device will indicate to the clinician if the intensity is outside of proper bounds by displaying a warning. The clinician should then adjust the probe until the warning disappears.
- The patient shall be instructed not to move, laugh, talk, etc. during the measurement. These actions can cause erroneous FlowMet-R measurements due to movement artifact. If this occurs, the measurement will need to be repeated and this should be noted in the CRF.
- Following the 30 second equilibration period, the clinician will then record FlowMet-R blood flow data for approximately 30 seconds using the data acquisition software, which will save the data on the local hard drive. Once data collection is complete, the clinician will note the “flow value” and waveform fidelity displayed in the software on the CRF.
- A post-hoc data quality check must be performed before taking the next flow measurement. Data fidelity will be assessed by observing the recorded waveform using the analysis tab of the software. The flow waveform should appear periodic without large unexpected spikes (indicating motion artifact) or sections that are missing (indicating over- or under- exposure). See Figure 3 (top) for examples of high quality flow waveform data and compromised data. In cases of advanced disease, the waveform may be severely damped or not be present at all. In cases where advanced disease has occluded blood flow and a waveform is not expected, the user will check the flow measurement to ensure the flow graph is relatively flat and there are no major motion artifacts in the flow recording. See Figure 3 (bottom) for examples of high quality and compromised data from patients with advanced disease.
- If the post-hoc data quality check reveals poor quality or missing data, steps 2-5 must be repeated until acceptable data has been recorded. This may require a repositioning of the probe. If 5 or more repeated attempts are made and poor quality data persists, the clinician will choose the optimal record to the best of their knowledge.

Figure 3: Example illustrations of high fidelity flow measurements (left column) compared with flow measurements that are corrupted by artifact (right column).

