8.4 Exclusion Criteria

Candidates for this study who meet any of the following criteria at the time of the baseline visit are NOT eligible to be enrolled in this study:

PAD Positive Cohort Exclusion

- Subject is under 40 or unable to consent.
- Subject has any medical condition, which, in the judgment of the Investigator and/or designee, makes the subject a poor candidate for the investigational study.
- Subject is excluded from analysis if no stenosis is found during Doppler but Tibial disease is suspected and Tibial ultrasound is not able to be performed.
- Subject does not have a suitable finger to attach the FlowMet-R probe.
- Subject does not have a suitable 1st or 2nd digit to attach FlowMet-R probe on the limb of interest.
- Subject has undergone revascularization within the last 90 days

- Subject cannot lay safely in a supine position.

Healthy Cohort Exclusion

- Subject is under 40 or unable to consent.
- Subject has any medical condition, which, in the judgment of the Investigator and/or designee, makes the subject a poor candidate for the investigational study.
- One or more limbs has a prior or current diagnosis of PAD, or is reasonably suspected of having a diagnosis of PAD.
- Subject does not have a suitable finger to attach the FlowMet-R probe.
- Subject does not have a suitable 1st or 2nd digit to attach FlowMet-R probe.
- Subject has undergone revascularization within the last 90 days

9. Study Procedures

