9.8 Intraprocedural Data Collection

Patients enrolled in the study who undergo revascularization surgery to address PAD/CLI will have pertinent data collected immediately before, during, and immediately after the surgical procedure. The schedule of events is summarized in Event Schedule B above (section 9.1). The following steps shall be followed:

- Prior to the start of the procedure, the FlowMet-R probe will be attached to the upper extremity for a 30-second recording. Next, the probe will be moved to the great toe of the limb being treated. If this digit is not usable, another digit may be used.
- Once the probe is placed on the digit, flow will be allowed to equilibrate for 30 seconds before checking signal quality to allow transient changes in perfusion to diminish. Signal quality will be

confirmed by observing the presence of a pulse waveform (if one is expected), or by the stability of the flatline (in the case of complete occlusion). The clinician will also ensure that an appropriate amount of light is detected by the FlowMet-R device. The following light intensity values are acceptable: maximum intensity greater than 30 but less than 255 and average intensity greater than 25 but less than 200. The FlowMet-R device will indicate to the clinician if the intensity is outside of proper bounds by displaying a warning. The clinician should then adjust the probe until the warning disappears. After proper placement and collection of the FlowMet-R and sensor have been confirmed, the physician shall be blinded to all outputs during and after the course of the intervention.

- Movement of FlowMet-R probe should be minimized during the procedure to prevent motion artifact and measurement errors.
- If the FlowMet-R probe is accidentally removed during the procedure or if a data quality warning is displayed by the FlowMet-R software (i.e. too much or too little light is being detected), the probe shall be replaced or reseated on the digit it was originally placed on (if possible). If this is not possible, a different digit may be used and this change shall be noted.
- The digit being measured and patient ID should be entered into the Patient Data section of the FlowMet-R software.
- FlowMet-R data saving shall be initiated prior to state of surgery. Therapies and notable events for each procedure, including timing, shall be recorded.
- The surgical procedure shall take place as per the standard of care.

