4.1.1.1.1 Definitions of PAD and CLI

- Two types of positive diagnosis of PAD will be explored according to published literature: (1) $ABI \leq 0.9$ or $ABI > 1.4$ and secondary verification of $TBI \leq 0.7$ with exhibition of at least mild claudication (Rutherford Category > 0), or (2) $ABI \leq 0.9$ or $ABI > 1.4$ and secondary verification of $TBI \leq 0.7$ without exhibition of symptoms. In either case, if the patient displays normal ABI but PAD is suspected, then a postexercise ABI will be performed using a 1-minute treadmill test or heel-raises. A postexercise drop of $ABI \geq 20\%$ or pressure drop $\geq 30\text{mmHg}$ will be considered a positive diagnosis [12].
- A positive diagnosis of CLI will be defined by exhibition of chronic rest pain and active wounds, verified by $TBI < 0.3$.
- Patients that are enrolled in the PAD positive cohort but are not positively diagnosed for PAD using the above definition (either because their disease is improving or they were screened incorrectly) will be considered PAD negative (see Section 7.11 for change to planned analysis).

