4.1.2.1 Secondary Endpoints

- Utilize FlowMet-R data to create a predictive model for the prognosis of vascular intervention within a three and six month timeframe from initial visit.
- Employ the predictive model of PAD severity to generate an ROC curve for diagnosis of significant stenosis (>50%) in the iliac, femoral, popliteal, peroneal, or tibial arteries.
- Conduct a correlation test between the predictive model of PAD severity and greatest percent stenosis in the iliac, femoral, popliteal, peroneal, or tibial arteries.
- Conduct a correlation test between changes in the predictive model of PAD severity and corresponding changes in ABI, TBI, and Rutherford Classification between any two study time points.

5. Investigation Plan

This study is a non-randomized, multi-center, longitudinal study of healthy subjects and subjects with PAD who are scheduled for ABI, TBI, and either Duplex ultrasound or Angiographic assessments in a vascular clinic. Subjects will first be evaluated for study inclusion/exclusion. If the subject meets the inclusion criteria and wishes to enroll in the study, they will be asked to sign an informed consent form (ICF) and considered for enrollment. If the subject meets inclusion criteria and is enrolled, the subject will undergo approximately 3 minutes of FlowMet-R blood flow measurements in addition to their routine standard of care examination.

Subjects enrolled in the PAD cohort will be assessed according to Event Schedule A in the clinical investigation protocol (CIP) at approximately 0, 3 months, and 6 months. Subject follow ups must meet the scheduled time window within +/- 30 days. Subjects that require a vascular (re)intervention for PAD-related treatment before the final measurement (6 month follow up) will have pertinent data collected and saved in the study registry. The vascular procedure may change the timing with respect to the amount of months after baseline that the follow up visits occur. In that case, the standard of care follow up visits post intervention will be adhered to, and data will be collected from the follow up visits that correspond most closely to timepoints at 3 and/or 6 months post baseline visit.

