7.2 General Methodology

Data analysis will be performed by Medtronic employed statisticians/programmers. All statistical analyses will be generated using SAS version 9.4 or later or R version 4.1 or later software. Demographic and baseline characteristics will be summarized descriptively and will include age, gender, ethnicity, race, body mass index and hemodynamic measures (ABI, TBI, and acceleration time from the FlowMet-R device). For continuous variables, descriptive statistics will be presented including the number of

subjects with the measurement, mean, standard deviation, median, minimum and maximum. For categorical variables, descriptive statistics will include the number with the characteristic, the number evaluated, and the percentage.

Subject enrollment and accountability, visit attendance, and end of study status will be displayed using a STROBE like diagram and descriptive statistics, as appropriate. For each study visit, the following information will be tallied: completed visits, missed visits, deaths (if any), study withdrawals, and lost to follow-up. Compliance with study visits will be summarized as the percent of subjects available at each visit.

Missing data for endpoints may result from clinical assessments that were unable to be performed or data missing from the FlowMet device. These missing values will be excluded from summaries and analyses. In general, efforts will be made to minimize missing data and imputation of missing data will not be performed.

The objectives are not hypothesis-driven and therefore their results will be presented descriptively with no adjustments for multiple comparisons.

The value from the predictive model from the FlowMet-R measurements will be derived by the Research and Development team and will consist of the acceleration time.

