7.8 Acceleration Time Values

Acceleration time will be derived by the Research and Development Team based on data from the FlowMet device. Data should be merged based on the subject identifier, visit (0, 3, or 6 months), and limb.

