7.10 Evaluation of Objectives

7.10.1 Primary Objectives

The primary objectives will compare the 95% CI of the AUC from the ROC curve to a value of 0.5 at 0-, 3-, and 6-months for the two definitions of PAD and one definition of CLI using the acceleration time from the FlowMet-R device. The 95% CI will not be corrected for repeated measures within a participant. If the 95% CI of the AUC excludes 0.5 at all time points for PAD or CLI, the acceleration time from the FlowMet-R device will be considered predictive of the respective endpoint. The 95% CI of the AUC will be derived using the method described in DeLong, et al (1998) [15]. Note, the definition of PAD will be defined two ways and analyzed separately. Definitions of PAD and CLI are provided in Section 4.1.1.1.1.

Three supplementary summaries will be computed. The sensitivity and specificity will be computed by selecting the point on the ROC curve closest to the upper left corner. Accuracy will be computed as the number of limbs correctly diagnosed divided by the total number of limbs.

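### The 2nd toe may replace the great toe, but the SAP makes no use of which toe was read, so a toe difference tied to disease could shift the CLI AUC in either direction

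*Protocol*

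**What the plan says.** Protocol 9.6 puts the probe on the great toe, with one exception: "if the great toe is not available the 2nd toe may be used, and this will be noted in the CRF". Protocol 8.4 excludes on digits only as follows: "Subject does not have a suitable 1st or 2nd digit to attach FlowMet-R probe on the limb of interest". A limb with a usable 2nd toe and no usable great toe therefore stays in.

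SAP 7.2 says that the value from the predictive model "will be derived by the Research and Development team and will consist of the acceleration time". SAP 7.8 says how that value joins the clinical data: "Data should be merged based on the subject identifier, visit (0, 3, or 6 months), and limb". The measured digit appears nowhere in the SAP's analyses.

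Neither document has a same-toe rule for the scheduled visits. Protocol 9.8 does have one for the interventional registry: a displaced probe goes back on its starting digit when that can be done, and a change of digit is noted.

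The analyses affected are these:

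- **CLI class** (SAP 4.1.1.1.1): "A positive diagnosis of CLI will be defined by exhibition of chronic rest pain and active wounds", with a low TBI as verification.
- **Primary rule** (SAP 7.10.1): "If the 95% CI of the AUC excludes 0.5 at all time points for PAD or CLI", acceleration time is called predictive.
- **Change endpoint** (SAP 4.1.2.1): "Conduct a correlation test between changes in the predictive model of PAD severity and corresponding changes in ABI, TBI, and Rutherford Classification". The method text in SAP 7.10.2, items 3 and 4, instead correlates acceleration time itself with those changes.

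**The concern.** Active wounds are part of the CLI definition, so the great toe may be unusable more often in CLI limbs than in healthy limbs. If acceleration time also differs between the two toes for reasons other than perfusion, part of what the CLI curve separates is great-toe from 2nd-toe recordings. Neither document reports a comparison of the toes, so neither shows that they are interchangeable.

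The same applies over time. Without a same-toe instruction, a limb may be read on one toe at baseline and on the other later. Where a change in the device value is analysed, that switch is part of the change.

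At stake is the interpretation of a primary AUC, on a point that data already recorded could settle. Left until after the results, it would become a post hoc argument over whether the CLI result reflects perfusion or digit.

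**Working it through.** **1. The plan's own figure.** The part of the sample size that bears here is 100 CLI limbs v 160 controls. Inputs: pilot CLI AUC 0.80 less the planning margin 0.2, giving 0.60 (SAP 6); null 0.5 (from SAP 7.10.1, since SAP 6 names none); two-sided alpha 0.05; power 0.8; control-to-case ratio k = 1.6. The binormal variance is V = 0.0099 exp(-a²/2)[(5a²+8) + (a²+8)/k], with a = 1.414 Φ⁻¹(AUC).

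- V at 0.50 = 0.0099 × 13 = 0.1287. V at 0.60 (a² = 0.128) = 0.1274.
- n = (1.96√0.1287 + 0.842√0.1274)² / 0.10² = 101, against 100 stated. It reproduces.

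**2. Assumed inputs.** The documents give neither the 2nd-toe shares nor the toe difference. I take a share q = 10% to 30% in CLI limbs, s = 2% in controls, and a shift d = -0.5 to +1.0 SD (positive towards disease). Readings are normal with unit SD, limbs are independent, and one visit is considered.

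**3. Effect on the AUC.** With m = √2 Φ⁻¹(true AUC):

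mixed AUC = [qs + (1-q)(1-s)] Φ(m/√2) + q(1-s) Φ((m+d)/√2) + s(1-q) Φ((m-d)/√2)

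At a true AUC of 0.50 this reduces to 0.5 + (q-s)[Φ(d/√2) - 0.5]. With q = 30% and d = +1.0 it is 0.5 + 0.28 × 0.260 = 0.573. With d = -0.5 it is 0.5 - 0.28 × 0.138 = 0.461. At a true AUC of 0.80, q = 30% and d = -0.5, it is 0.692 × 0.800 + 0.294 × 0.687 + 0.014 × 0.884 = 0.768.

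| True AUC | q | d = -0.5 | d = +0.5 | d = +1.0 |
|---|---|---|---|---|
| 0.50 | 10% | 0.489 | 0.511 | 0.521 |
| 0.50 | 30% | 0.461 | 0.539 | 0.573 |
| 0.80 | 10% | 0.790 | 0.806 | 0.809 |
| 0.80 | 30% | 0.768 | 0.823 | 0.837 |

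With d = 0 nothing moves. With equal shares in both classes (20% and 20%), a true AUC of 0.50 stays at 0.50.

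**4. Effect on a single CI.** The Hanley-McNeil SE for 100 v 160 is 0.037 at AUC 0.50 and 0.030 at 0.80.

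- True AUC 0.50: the chance that the CI lies wholly above 0.5 is 1 - Φ(1.96 - z), with z = shift/0.037, against a nominal 2.5%. It is 4.8% for q = 10%, d = +0.5; 18% for q = 30%, d = +0.5; 51% for q = 30%, d = +1.0; and 0.1% for q = 30%, d = -0.5.
- True AUC 0.60 (the planning bound), q = 30%: power falls from 0.78 to 0.63 at d = -0.2 (AUC 0.584) and to 0.38 at d = -0.5 (AUC 0.561).
- True AUC 0.80: the lowest value in the table, 0.768, has SE 0.031, so its lower limit is about 0.71, far above 0.5.

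**5. Change analyses, if change in the device value is used.** Suppose a share p = 5% to 15% of pairs switch toe in random direction, and the between-toe SD equals the SD of true change. Then r is multiplied by 1/√(1+p), that is 0.98 to 0.93. If switching goes with worsening disease, the effect need not be simple attenuation.

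**6. Cost of a great-toe-only run.** At q = 30% the CLI limbs fall from 100 to 70. At AUC 0.60 the SE rises from 0.037 to 0.041 and power falls from 0.78 to 0.67.

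**The case against.** The other side has several sound points.

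- **The merge.** A reader might infer from SAP 7.8 that the digit is discarded. The text does not support this. It lists join keys, a join keeps its other columns, and with one toe planned per limb and visit those keys already identify the record. The gap is that no analysis uses the digit.
- **The false-positive figures.** A reader might take 18% or 51% as the chance of a false CLI claim. They rest on assumed shares, a positive shift, a true AUC of 0.50 and one visit. The rule needs all three visits, and healthy subjects are measured only once, so the control share describes baseline at most. At follow-up the comparison limbs come from the PAD cohort.
- **The change analyses.** A reader might conclude that a toe switch is analysed as a change in flow. That holds under the endpoint wording in SAP 4.1.2.1. SAP 7.10.2 as written uses acceleration time itself, so no between-visit difference in the device value is computed.
- **The link to disease.** The documents do not say that 2nd-toe use is commoner in CLI, and the definition does not place the wounds on the toe. The link is plausible, not documented.
- **The test as used.** Substitution belongs to the procedure and to eligibility, so the mixed AUC validly describes that use. It is still not a great-toe AUC.

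These points limit the size of the concern. They do not remove it: a difference that may follow disease class can enter a primary AUC without being seen.

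**Conclusion.** The point holds as a minor analysis gap. The 2nd toe is allowed, no same-toe rule covers the scheduled visits, and the SAP leaves the digit unused. Under the assumptions above, the CLI AUC moves by about -0.04 to +0.07 if the true value is 0.50 and by about -0.03 to +0.04 if it is 0.80.

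At the pilot AUC of 0.80 the conclusion against 0.5 would not change. Near 0.5, or at the planning bound of 0.60, it could. The documents do not support saying that the AUC is biased, or biased upwards: neither the toe difference nor its sign is known, and with no toe difference there is no bias.

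**What to change.** - **SAP 7.8:** keep the merge key and carry the digit as a variable from the CRF. Making it a key would risk losing records with a missing or mismatched digit label, because the SAP uses complete cases.
- **SAP 7.10.1:** report 2nd-toe use by diagnostic class and visit, and add a supporting AUC on great-toe recordings only. Compare its estimate and CI with the main analysis. Do not judge it by whether significance is kept, since it loses CLI limbs and precision.
- **SAP 7.10.2:** reconcile the endpoint wording (change in the model output) with the method wording (acceleration time itself). Where change is analysed, add a supporting analysis of pairs read on the same toe.
- **Protocol 9.6:** ask for the same toe at each visit where usable, in line with the registry instruction in 9.8.

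The cost is some SAP and protocol wording and a repeat run of the same code; substitution is already noted on the CRF. The downside is fewer limbs in the supporting runs, mainly CLI limbs.

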4.1.1.1.1 Definitions of PAD and CLI

- Two types of positive diagnosis of PAD will be explored according to published literature: (1) $ABI \leq 0.9$ or $ABI > 1.4$ and secondary verification of $TBI \leq 0.7$ with exhibition of at least mild claudication (Rutherford Category > 0), or (2) $ABI \leq 0.9$ or $ABI > 1.4$ and secondary verification of $TBI \leq 0.7$ without exhibition of symptoms. In either case, if the patient displays normal ABI but PAD is suspected, then a postexercise ABI will be performed using a 1-minute treadmill test or heel-raises. A postexercise drop of $ABI \geq 20\%$ or pressure drop $\geq 30\text{mmHg}$ will be considered a positive diagnosis [16].
- A positive diagnosis of CLI will be defined by exhibition of chronic rest pain and active wounds, verified by $TBI < 0.3$.
- Patients that are enrolled in the PAD positive cohort but are not positively diagnosed for PAD using the above definition (either because their disease is improving or they were screened incorrectly) will be considered PAD negative but will not be grouped into the healthy cohort.

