9.7.3 Postexercise ankle brachial index (ABI)

If an enrolled patient's ABI and TBI measurements classify that patient as not having PAD/CLI as per the definitions in Section 8.4, but it is suspected that the patient may have PAD based upon medical history or clinical symptoms, a postexercise ABI measurement will be performed. For such patients, guidelines

provided by the ACC/AHA will be followed. A treadmill or heel-raise test will be considered an acceptable challenge for measurement of postexercise ABI.

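### Independence of FlowMet-R and the reference standard is not ensured at the diagnostic visits: flat-trace acceptance depends on expected disease, and nothing shields the postexercise ABI decision from the trace

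*Protocol*

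**What the plan says.** **Accepting a trace (Protocol 9.6).** The live check for a pulse is conditional: "Signal quality will be confirmed by observing the presence of a pulse waveform (if one is expected"). A limb without a pulse has a separate route, again tied to disease: "or by the stability of the flatline (in the case of complete occlusion"). On review of the recording, the waveform should look periodic, with an exception: "In cases where advanced disease has occluded blood flow and a waveform is not expected, the user will check the flow measurement" to see that it is flat and free of motion artifact. Poor or missing data means repeating the measurement. After five or more attempts, "the clinician will choose the optimal record to the best of their knowledge".

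**Order and visibility (Protocol 9.6).** "FlowMet-R measurements will be taken before noninvasive testing as detailed in Event Schedule A". The clinician then notes the flow value and the "waveform fidelity displayed in the software on the CRF".

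**Postexercise ABI.** Protocol and SAP 4.1.1.1.1 say that "if the patient displays normal ABI but PAD is suspected, then a postexercise ABI will be performed", and a sufficient drop makes the limb PAD positive. No basis for the suspicion is given there. Protocol 9.7.3 does give one: resting ABI and TBI do not classify the patient as PAD/CLI, "but it is suspected that the patient may have PAD based upon medical history or clinical symptoms".

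**Masking.** Protocol 5 and 9.8 mask staff to FlowMet-R output during interventional procedures. Nothing similar is stated for the baseline, 3-month or 6-month diagnostic visits.

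**The concern.** A diagnostic accuracy estimate assumes that the index test is obtained without reference to disease status, and that the reference label is assigned without reference to the index test. The plan leaves an opening on each side.

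- **Index side.** Two limbs giving the same flat trace can be handled differently, depending on whether the operator thinks the limb is severely diseased.
- **Reference side.** For a limb with a normal resting ABI, the label turns on whether a second test is done, and by then the trace has been read.

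The primary result is at stake. SAP 7.10.1 asks whether the 95% CI of the AUC excludes 0.5 at all three time points, for two PAD definitions and one CLI definition.

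**Working it through.** The plan gives no figure to reproduce. Part (a) is a comparison of the text; part (b) is a calculation on assumed inputs.

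**(a) Flat traces**

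1. Both checks in Protocol 9.6 (live and on review) pass a flat trace only when disease explains it. Otherwise the trace fails the pulse or periodicity check and is repeated.
2. No section defines when a pulse is expected, and none hides cohort, Rutherford category or wounds from the operator.
3. Rutherford category is part of PAD definition 1; rest pain and wounds are part of the CLI definition (4.1.1.1.1). Acceptance can therefore use facts that also determine the label.
4. The direction is not determined. If repeats replace flat traces mainly in limbs thought healthy, the groups may separate further. But the SAP predictor is acceleration time (SAP 7.2, 7.8, 7.10.1), which is not defined. If a flat trace yields no value (assumption), accepted flat traces in the worst limbs are dropped as missing (SAP 7.2, 7.4), which may pull the other way. The documents do not allow the effect to be sized.

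**(b) Postexercise ABI**

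From the documents: 240 PAD limbs and 160 control limbs. Assumed:
- a share s of the 400 limbs are PAD-cohort limbs that are normal at rest, taken from the 240;
- half of these would be positive on exercise, regardless of trace;
- half are tested overall, and untested limbs count as PAD negative;
- worse-than-median traces are tested with probability 0.5 + b and the others with 0.5 − b, where b = 0.25 is partial (75% v 25%) and b = 0.5 is full (100% v 0%).

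Take a device with no true discrimination. With u = 400s, u/4 limbs are labelled positive, with mean trace percentile 0.5 + b/2. The other 3u/4 are labelled negative, with mean percentile 0.5 − b/6. The totals are P = 240 − 3u/4 and N = 160 + 3u/4, so

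AUC shift = (u/4)/P × b/2 + (3u/4)/N × b/6 = (u·b/8)(1/P + 1/N).

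| s | u | P | N | b = 0.25 | b = 0.5 |
|---|---|---|---|---|---|
| 5% | 20 | 225 | 175 | 0.006 | 0.013 |
| 10% | 40 | 210 | 190 | 0.013 | 0.025 |
| 20% | 80 | 180 | 220 | 0.025 | 0.051 |
| 30% | 120 | 150 | 250 | 0.040 | 0.080 |

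For example, s = 30% and b = 0.25 gives 3.75 × (1/150 + 1/250) = 0.040.

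A simulation (500 runs per cell, true AUC 0.50, 0.67 and 0.80) agrees: 0.006 to 0.041 for partial and 0.011 to 0.081 for full trace-driven testing. With no true discrimination, 0.50 becomes 0.505 to 0.581.

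For scale, the Hanley–McNeil 95% half-width at AUC 0.60 with 240 v 160 limbs uses Q₁ = 0.6/1.4 = 0.4286 and Q₂ = 0.72/1.6 = 0.45. The variance is [0.24 + 239 × 0.0686 + 159 × 0.09]/38,400 = 0.000806, and 1.96 × √0.000806 = 0.056.

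Follow-up visits may be more exposed. Healthy subjects attend once, so unless their baseline values are reused, the negatives at 3 and 6 months come only from the PAD cohort. A separate simulation of full trace-driven testing, with an assumed 180 positives, 25 negatives and 20 uncertain limbs, moves the AUC from 0.673 to 0.704.

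If testing ignores the trace, b = 0 and the shift is zero.

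**The case against.** A reader might infer that suspicion of PAD is formed from the trace, that the probe operator also orders the postexercise test, and that both routes inflate the AUC. The documents support none of these.

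- Protocol 9.7.3 bases suspicion on history or symptoms, which can predate the measurement. The device-risk table in Protocol 6.2 rules out using FlowMet-R data for diagnosis. PAD-cohort patients are generally already under suspicion (Protocol 8.1), and healthy subjects are by definition not (8.3).
- No section says who decides on the postexercise ABI.
- Repeats are not open-ended, and the light-intensity, spike and missing-section checks do not depend on disease status.
- Taking FlowMet-R first has a benefit: the operator has not yet seen that visit's ABI/TBI. Resting ABI/TBI is normally automated (9.6.1.2), and the CLI definition does not use the postexercise route.
- In many of the assumed scenarios the shift lies inside the 0.056 half-width.

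All of this stands, and it limits the point to independence that is not ensured. It does not remove the point. The flat-trace rule is written text. Nothing requires suspicion to be recorded before the trace, and 4.1.1.1.1, which governs the label, gives no basis for it. The event schedules are figures that could not be read here and may add ordering or masking details.

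**Conclusion.** The point holds as a lack of protection. It is minor and cheap to correct.

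(a) Acceptance of a flat trace depends on presumed disease status. This can bias the AUC for PAD and CLI; direction and size are unknown.

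(b) The trace could influence which limbs with a normal resting ABI get a postexercise ABI. This concerns the two PAD definitions only. The shift is zero if the basis in 9.7.3 is followed without regard to the trace, about 0.01 to 0.04 under partial trace-driven testing, and up to 0.08 if testing follows the trace fully and 30% of limbs are normal at rest. The share of such limbs, the exercise-positive rate and the testing pattern are all assumptions; the documents give none of them.

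The stronger statements, that the two tests are dependent or that the AUC is inflated, are not established.

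**What to change.** 1. **Trace rule (Protocol 9.6).** Replace all three status-dependent clauses: the expected-pulse condition and the complete-occlusion condition in the live check, and the advanced-disease exception on review. Removing only the first would leave the other two in force. Use one rule for every limb, with the same light-intensity and motion limits and the same number of repeats for a flat trace. Save all attempts, and report attempts and flat traces by group.
2. **Suspicion of PAD.** Add a yes/no CRF entry per limb, based on history or symptoms and completed before the probe is placed. Let only that entry decide which postexercise results count in the reference label. Testing done for clinical care is unaffected.
3. **Trigger wording.** Reconcile 4.1.1.1.1 (normal ABI) with Protocol 9.7.3 (ABI and TBI together). The latter also points for its definitions to Section 8.4, which lists exclusion criteria.
4. **SAP.** Add a sensitivity analysis that labels PAD from resting ABI/TBI only. It shows how far the result depends on the postexercise route. A difference is not all bias, because limbs positive only on exercise become negatives.

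Cost: one CRF field, a protocol amendment needing IRB approval, and a few more minutes for flat traces. If enrolment is complete, item 4 and the reporting by group, as far as attempts were recorded, can still be done.
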